Demographically similar pediatric patient groups with varying levels of exposure to the FVPP at baseline will be compared: high exposure (>24 months), moderate exposure (12-24 months), and no previous exposure. Children with no previous exposure will be introduced to the FVPP, and researchers will track changes in dietary intake, food security, and weight status over two years. The specific aims of the study are to (1) compare baseline dietary intake, food security, and weight status between pediatric patients with varying levels of exposure to the FVPP; (2) measure changes in diet, food security, and weight status before and after never-before-exposed children are introduced to the FVPP; and (3) compare mean 12- and 24-month follow-up measures of dietary intake, food security, and weight status in the initial no exposure group to baseline measures in the high exposure group. A central expectation is that greater exposure to this FVPP will promote intake of fruits and vegetables, better food security, and lower rates of childhood obesity.

The current study, in design and approach, is grounded in the theoretical framework of Bandura's Social Cognitive Theory (SCT). SCT explains behavior using a three-stage, dynamic model linking personal factors, environmental factors, and behavior.^{30,31} This study's SCT framework involves collaborations with partnering physicians and local agricultural leaders to support environmental change and social learning. Since children's dietary intake is generally guided by their parents, critically important environmental factors, such as access to fruits and vegetables as well as caregiver modeling of the healthy behaviors, are of particular importance.^{32,33} Consistent with SCT, we also posit that self-efficacy is central to behavior change. Accordingly, self-efficacy for consuming fruits and vegetables, which refers to one's judgment over one's capability to enact the behavior, is important to change dietary behavior.³⁴ By grounding the study with the theoretical framework of SCT, we suggest that pediatrician issuance of a prescription for fruits and vegetables to every child at each office visit will promote food access and self-efficacy to consume healthy foods. Furthermore, pediatrician messaging to children and caregivers will influence health-promoting behaviors linked to increased consumption of fruits and vegetables.

Study Design

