This study will include a cross-sectional analysis of data from a consecutive sample of caregiver-child dyads with varying levels of exposure to a fruit and vegetable prescription program (FVPP) that provides one \$15 prescription for fresh produce to every child during pediatric office visits. Considering the importance of dietary patterns during childhood on long-term diet and health¹¹⁻¹³ alongside evidence that indicates adolescence is the specific period when food insecurity has the greatest potential to negatively impact the diet,³⁵ data collection and analyses will focus specifically on children and adolescents ages 8-16 years. A total of 700 caregiver-child dyads (one caregiver and one child per household) will be enrolled in the study, with approximately 200 dyads enrolled at clinic 1 (high exposure); 200 dyads enrolled at clinic 2 (moderate exposure), and 300 dyads enrolled at clinic 3 (no previous exposure to the FVPP). A description of the clinics is provided with our explanation of the 'Setting' for this study.

Dyad enrollment will be based on exposure to the FVPP as defined by caregiver-reported and clinic-verified length of time that the participating child has been a patient at one of three partnering clinics. Accordingly, we expect dyads to cluster based on pediatric clinics as follows: clinic 1 (high exposure), clinic 2 (moderate exposure), and clinic 3 (no previous exposure). A sample of approximately 200 pediatric patients newly exposed to the FVPP at clinic 3 will be followed for a period of two years as part of a non-controlled longitudinal intervention trial that will examine changes in dietary patterns, food security, and weight status over time.

Setting

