- Clinic 3 is the largest pediatric clinic in Genesee County, with Flint as its urban center. Expansion of the FVPP to clinic 3 will substantially increase program reach among vulnerable children and families living in Flint. Last year, clinic 3 had over 12,000 pediatric visits. It has a comparable patient population to clinics 1 and 2, serving only children in need who are residents of Genesee County.

Participants and recruitment

A sample of 250 caregiver-child dyads presenting at clinic 1, 250 caregiver-child dyads at clinic 2, and 350 caregiver-child dyads at clinic 3 will be assessed for eligibility, with 700 total dyads enrolled (anticipated 10-15% not meeting eligibility and 10% refusal based on a previous study). To control for confounders, we will adopt a balancing strategy that consists of recruiting in the study children who have approximately the same age, sex, and race across the three clinical settings. These children will not be balanced according to variables pertaining directly to the exposures (e.g., duration of FVPP exposure).

With target samples of 200, 200, and 300 caregiver-child dyads enrolled in clinic 1 - high exposure, clinic 2 - moderate exposure, and clinic 3 - no previous exposure, respectively, we have well above 90% power to jointly detect modest relative differences in the baseline mean intake of vegetables of 20% from clinic 2 to clinic 3 and 38% from clinic 1 to clinic 3. This calculation assumes an underdispersed Poisson model with a dispersion parameter of 0.82, derived using previously published data on the mean intake of vegetables of 0.72 cup and a standard deviation of 0.77 cup in the settings with no prior FVPP exposure.²⁰ Likewise, with 300 caregiver-child dyads enrolled in clinic 3, we have well above 90% power to detect a modest temporal improvement in the mean intake of vegetables of 25% over 12 months (0.72 cup at baseline versus 0.90 cup at 12-month follow-up). This calculation assumes a correlated Poisson model for underdispersed count data with timepoint dispersion parameter of 0.82, and a modest temporal correlation of 0.2. Increasing values of the temporal correlation greatly improves the statistical power. Finally, estimation of FVPP effects will specify two-tailed tests with alpha set at the 0.05 level.

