Inclusion criteria for all participants include a restriction to children aged between 8 and 16 years at enrollment; the caregiver and child must speak English. An estimated 2% of the Flint population cannot speak English. A legal guardian must be present at enrollment and must sign an informed consent document; each child must assent to participation. Inclusion criteria for clinic 1 (high exposure) will include participation in the FVPP for over 24 months. Inclusion criteria for clinic 2 participants (moderate exposure) will include participation in the FVPP for 12 to 24 months. Inclusion criteria for clinic 3 participants (no exposure) will include no previous exposure to the FVPP. Potential participants at clinic 3 will be excluded if the household includes a sibling who already enrolled in the research study or if there has been movement of the patient from one clinic to another clinic (<3% of patients).

Fruit and Vegetable Prescription Program (FVPP)

Fruit and vegetable prescriptions, analogous to medical prescriptions, are electronically prescribed by pediatricians and given to patients. They are intended to promote a healthy food environment within the home.⁴¹ For our study, eligible vendors comprise the downtown Flint Farmers' Market (FFM) and Flint Fresh, a mobile market and food hub that offers locally grown, home-delivered, fresh produce boxes. Vendors accept the prescriptions (\$15 each) as if they were gift certificates or vouchers for any fresh fruits or vegetables. In partnership with FFM and Flint Fresh, prescription redemption rates are recorded and tracked. Over time, the redemption of prescriptions has been increasing (from under 30% when the program was initiated to its current redemption rate of approximately 50%).

Clinics 1 and 2 have developed an efficient and reliable method to record and track prescription distribution rates. Fruit and vegetable prescriptions are built using the Epic electronic medical record (EMR) system, to order and print each prescription, and to track individual and aggregate monthly distribution rates. Key personnel on the current study will train pediatricians and staff at clinic 3 regarding EMR procedures to order, print, and track prescriptions through their EMR system, eClinicalWorks (eCW). The study protocol will capture monthly reports that cover topics such as the number of patients seen in the clinic and prescriptions distributed.

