Reasonably Foreseeable Risks

There are no known risks to participants.

Primary outcome measures

Child dietary patterns

Because the children's dietary patterns across gradients of exposure to the FVPP are of primary interest, we will administer two non-consecutive 24-hour dietary recalls and one validated food frequency screener. The dietary recall data will cover the 24 hours before enrollment and a second 24-hour interval that occurs just before a post-baseline assessment completed by the RA within seven days after baseline. The Automated Self-Administered 24-Hour (ASA-24) Dietary

Assessment Tool will be used for these assessments. The 24-hour dietary recall is a valid measure for assessing the dietary intake of children ages eight years and older.⁴⁹ The RA also will administer Block Kids Food Screener, a food frequency questionnaire, to allow for the assessment of usual and long-term eating behaviors with relatively little administration burden. Block Kids Food Screener has shown good relative validity for children and adolescents.⁵⁰ Its 41 items assess the frequency and quantity in which foods and beverages were consumed over the previous week.

After data collection, a dietary analysis, using the Block Online Analysis System, will provide nutrient estimates and the number of servings by food group. We will use these data to evaluate the mean daily intake of total fruits and vegetables, total vegetables, total fruits, and whole fruits. The Healthy Eating Index (HEI) will be generated from the dietary data for use as a measure of the diet quality of the children.^{51,52}

Child-reported food security

Children ages 12 years and older will complete the Self-Administered Food Security Survey Module for Youth (SAFSSMY). Although the SAFSSMY was found to have adequate internal validity for children ages 12 years and older, it is not recommended for use with younger children.⁴⁷ The sum of affirmative responses (“a lot” or “sometimes”) to module questions will provide the child’s initial raw score on the perceived food security scale, with food security status assigned based on raw score (0-1=high/marginal food security; 2-5=low food security; 6-9=very low food security). This study’s sample size is sufficient for a confirmatory factor analysis based on Item Response Theory, which will be used to evaluate whether the unit weight assigned to each item can be improved upon.

Household food security

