An alternative balancing strategy based on propensity scores will be used to mitigate potential differences at baseline among participants in the three study groups. These scores will be used to derive an unbiased estimate of the average treatment effect of FVPP on study endpoints. The generalized propensity score to account for multiple levels of treatment in the spirit of Imbens will be estimated with a multinomial logistic regression.⁶² To estimate the FVPP effects, we will use an elaborated multinomial logistic model that includes the child's level, the caregiver's level covariates, and functions thereof (e.g., interactions).

The choice of analytic methods will be guided by the specific aims, the nature of study endpoints and that of relevant data. Independence models will be used to compare baseline dietary intake, food security, and weight status between pediatric patients with varying levels of exposure to the FVPP. Correlated data models will be used to evaluate (1) changes in diet, food security, and

weight status when never-exposed children are introduced to the FVPP; and (2) compare mean follow-up measures of dietary intake, food security, and weight status in the initial no exposure group to baseline measures in the high exposure group.

Comparison of baseline measures based on FVPP exposure

Multiple linear regression will be used to assess the relationship between mean daily intake of fruits and vegetables and level of exposure to the FVPP. A basic logistic regression model will be used to evaluate the adjusted effect of the child-level exposure to the FVPP on the obesity probability. An ordinal logistic regression model will be used to evaluate the adjusted effects of the child-level exposure to the FVPP on food security (measured as an ordinal outcome). Within this class of models, we will entertain the popular proportional odds model with prior evaluation of the assumption of the proportionality of odds across the ordered levels of food security. These analyses will be adjusted for variables such as food assistance program participation, nutrition education program participation, child race, child age, child gender, caregiver-reported income group, caregiver-reported weight status, caregiver education, and child-reported mean daily intake of fruits and vegetables.

Evaluation of changes when children are introduced to the FVPP

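### The Aim 1 regressions adjust for child-reported fruit and vegetable intake, which is the dietary outcome itself and, in the obesity and food-security models, a consequence of exposure

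*Combined protocol and SAP*

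**What the plan says.** The section on comparing baseline measures by FVPP exposure describes three models in turn. Multiple linear regression will "assess the relationship between mean daily intake of fruits and vegetables and level of exposure to the FVPP". Logistic regression handles obesity, and an ordinal logistic model handles food security. A single sentence then gives the adjustment variables for these analyses together. The list is introduced as illustrative, exempts no model, and closes with "caregiver education, and child-reported mean daily intake of fruits and vegetables".

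Four other places bear on that variable:

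- **Study aims and hypotheses.** The central expectation is that "greater exposure to this FVPP will promote intake of fruits and vegetables, better food security, and lower rates of childhood obesity".
- **Participants and recruitment.** "Inclusion criteria for clinic 1 (high exposure) will include participation in the FVPP for over 24 months". For clinic 2 the requirement is 12 to 24 months; clinic 3 has had none.
- **Primary outcome measures, child dietary patterns.** Intake comes from two 24-hour recalls around enrolment and the Block Kids screener. Of the screener the plan says "Its 41 items assess the frequency and quantity in which foods and beverages were consumed over the previous week". Intake is listed as a primary outcome.
- **Statistical analysis plan, opening paragraphs.** Regression adjustment is justified as control of confounders.

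**The concern.** Baseline in this design is not before exposure. For clinics 1 and 2 it falls after one or more years of the program, so anything the program changes has had time to change. By the plan's own hypothesis, intake is one of those things. The adjustment therefore does different damage in each model.

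1. **Dietary model.** The covariate is the outcome, or a second measurement of the same construct by the other child instrument. Holding it fixed removes the effect that the model is meant to estimate.
2. **Obesity model.** Intake is a plausible step between prescriptions and weight. Conditioning on it leaves only the part of the effect that does not run through diet, whereas Aim 1 asks for the whole difference between exposure levels.
3. **Food-security model.** Intake is again post-exposure. The Study Design section also treats diet as affected by food insecurity: "adolescence is the specific period when food insecurity has the greatest potential to negatively impact the diet". The model would then condition on a consequence of both exposure and outcome, which can create an association where none exists.

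Diet, food security and weight are all described under the primary outcome measures, so the main Aim 1 comparisons are affected.

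**Working it through.** **Inputs from the sample-size paragraph (Participants and recruitment).** The reference figures are "previously published data on the mean intake of vegetables of 0.72 cup and a standard deviation of 0.77 cup". Differences from clinic 3 are 20% (clinic 2) and 38% (clinic 1); n = 200, 200 and 300 for clinics 1, 2 and 3; alpha is 0.05, two-sided. These inputs are for vegetables only, whereas the Aim 1 model is for fruits and vegetables, so what follows is an illustration.

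**The plan's own figure first.**
- Dispersion: 0.77² / 0.72 = 0.823, matching the stated 0.82.
- Group means: 0.72, 0.72 × 1.20 = 0.864, and 0.72 × 1.38 = 0.994. The differences from clinic 3 are 0.144 and 0.274 cup.
- Joint 2-df Wald test on log means, variance 0.82/(n × mean): noncentrality 13.21, power 91.3%.
- Joint test on the linear scale with SD 0.77: noncentrality 15.44, power 95.0%.

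Both exceed 90%, in line with the plan's joint claim. Pairwise on the linear scale, SE = 0.77 × √(1/300 + 1/200) = 0.0703. Power is 97% for clinic 1 versus 3 and 53% for clinic 2 versus 3. The plan claims only joint power, so the 53% is context and not a separate fault.

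**Dietary model, same variable on both sides.** The fit is perfect, the covariate's coefficient is 1 and both exposure coefficients are exactly 0.

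**Dietary model, other child instrument as covariate.** Assume a covariate SD of 0.77, a within-group correlation r with the outcome, and group shifts equal to s times those of the outcome. The documents give neither r nor s.
- Adjusted difference = D × (1 − r × s), where D is the unadjusted difference.
- SE² = 0.77² × (1 − r²) × [1/300 + 1/200 + (sD)² / (697 × 0.77²)].
- Power from the noncentral t with 696 df.

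Example: for r = 0.3 and s = 1, 0.2736 × 0.7 = 0.192, SE = 0.0678, ratio 2.83, power 80.6%.

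| Clinic 1 vs 3 | r = 0.3 | r = 0.5 | r = 0.7 |
|---|---|---|---|
| s = 1: estimate (cup) | 0.19 | 0.14 | 0.08 |
| s = 1: power | 80.6% | 60.3% | 36.5% |
| s = 0.5: estimate (cup) | 0.23 | 0.21 | 0.18 |
| s = 0.5: power | 93.2% | 91.9% | 94.2% |

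Simulation with 6,000 replicates per setting gave 80.5, 60.9 and 36.1% for s = 1, and 93.2, 91.5 and 93.5% for s = 0.5.

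For clinic 2 versus 3, s = 1 gives 0.10, 0.07 and 0.04 cup with power 32, 22 and 14%. With s = 0.5 it is 0.12, 0.11 and 0.09 cup with power 42-46%.

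On the joint test, simulated power was about 94% without the covariate and about 70, 48 and 27% with it at s = 1 (400 replicates). The same formulas with a 2-df chi-square give 95.0%, then 72.5, 50.7 and 28.9%.

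**Obesity model.** For illustration, assume the whole effect runs through intake, with log-odds = −0.85 − 0.7 × (intake − 0.72). Averaging over the intake distribution gives obesity of 31.0% in clinic 3 and 27.3% in clinic 1, an odds ratio of 0.83. Conditional on intake, the odds ratio is exactly 1 by construction. A simulation of 400 replicates gave 0.85 without intake and 1.02 with it, consistent with these values within simulation error. The slope, intercept and full mediation are assumptions.

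**Food-security model.** Code the latent scale so that higher means more secure; the raw scores in the plan run the other way. The intake shift is 0.274 / 0.77 = 0.355 SD. With a within-group correlation rho between food security and intake, adjusted coefficient = total effect − rho × 0.355. For rho of 0.1, 0.2 and 0.3 the shift is −0.04, −0.07 and −0.11 SD. A true null would then look like harm. The linear latent scale and the values of rho are assumptions.

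**The case against.** The strongest reply is that the list is illustrative and shared across models, and that any analyst would drop the outcome from its own model. Only the obesity and food-security sentences speak of adjusted effects, which favours that reading. The perfect-fit case would never be reported, and using one instrument to adjust the other is not written in the plan; it is inferred from there being two instruments. This is fair, and it makes the dietary problem the easiest to avoid in practice. It does not help the other two models, where intake is expressly named.

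The power loss is also not inevitable. At r = 0.5 the ratio (1 − r × s)/√(1 − r²) exceeds 1 when s is below about 0.27, and at r = 0.7 when s is below about 0.41. Apart from the small extra variance term, power then rises. The estimate is still too small whenever r and s are positive.

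The food-security argument draws on a sentence written to justify the age range, not on a stated causal model. That weakens the direction and size given above, but not the fact that intake is measured after exposure.

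The plan also promises robustness analyses and a generalized propensity score that does not name intake. The propensity score is presented as an alternative strategy and does not correct the regressions.

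Finally, the clinics are not randomised, and current intake might stand in for earlier differences in diet. It does so only by mixing them with the program's effect. Other listed covariates are also collected at this visit, but they are not the dietary outcome that the central hypothesis says exposure will raise.

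**Conclusion.** The concern holds, and the list should be corrected before analysis. As written, the dietary comparison is degenerate or attenuated, the obesity coefficient is not the total effect of exposure, and the food-security coefficient can be biased in the absence of any effect. If the list is read as shared, with each outcome dropped from its own model, the last two problems remain.

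The direction of the dietary attenuation follows from the model when r and s are positive; its size does not. Depending on assumed r and s, the clinic 1 versus 3 estimate is 15% to 70% too small, and power lies between 36.5% and about 94%, against 97% without the covariate. The obesity and food-security figures are illustrations of mechanism only.

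The problem is confined to the Aim 1 regressions. The sections for Aims 2 and 3 do not repeat this list.

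**What to change.** Delete child-reported fruit and vegetable intake from the Aim 1 adjustment list, for all three models. As a precaution, add a sentence that it is not a covariate in the generalized propensity score model, where it is not named but could enter as a child-level variable. If an intake-adjusted obesity model is of interest, report it separately as an exploratory direct-effect or mediation analysis.

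The cost is one deleted phrase and one added sentence. Design, sample size and data collection do not change. There is a small downside: pre-exposure diet is not measured in clinics 1 and 2, so the main model gives up current intake as a rough proxy for earlier dietary differences. The exploratory model can show how far the obesity result depends on that.
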